9.4. Variables

Categories of variables to be abstracted from the medical records if available include, but are not limited to, the following (a detailed description of variables and timepoints will be provided in the SAP):

9.4.1. Demographic and Clinical Characteristics

Category	Variable	Timepoint
Demographics and medical history	Age (years)	Index date, closest assessment to index
	Sex: 
 • Male; • Female. 	
	Height (centimeters [cm] or feet ['] and inches ["], depending on the country)	
	Weight (kilograms [kg] or stones [st] and pounds [lb], depending on the country)	
	Ethnic/racial group (country-specific options to be used)	
	Smoking status: 
 • Current smoker; • Previous smoker; 	

Category	Variable	Timepoint
	
 Never smoked; Unknown. 
History of illicit drug use:
 
 Yes; specify drug (if documented); No; Unknown. 
If “yes” to history of illicit drug use, specify route of administration:
 
 Inhalation; Nasal administration; Intravenous injection; Intramuscular injection; Oral administration; Other (specify). 
History of alcohol abuse:
 
 Yes; No; Unknown. 	

Comorbid medical conditions
 
Note: this refers to comorbidities documented in the chart during the 30 days prior to index and the date of index. However, the onset of the comorbidity may have occurred prior to this.
	
 AIDS; Asthma; Autoimmune disease; Bronchiectasis; Chronic granulomatous disease; COPD; Congestive heart failure; Coronary artery disease; Cytomegalovirus infection; Diabetes mellitus or uncontrolled hyperglycemia; Drug-related AEs; Fever and neutropenia; Fungal infection, (specify: fungal, bacterial, other); Influenza; Iron overload; Liver cirrhosis; Graft-versus-host disease; Hematologic malignancy; Herpes virus (including VZV, CMV, etc.); Hypertension; Major trauma; 	30 days prior to index date, index date

Category	Variable	Timepoint
	
 • Moderate-to-severe renal disease; • Neutropenia; • Severe burns; • Solid tumor (specify); • Solid organ transplantation (specify); • Stem cell transplantation (specify); • Tuberculosis; • Other (specify); • Unknown. 	
Fungal disease characteristics	
Disease type
 
 • Invasive aspergillosis; • Mucormycosis. 
Date of suspected diagnosis (DD MMM YYYY) Date of confirmed diagnosis (DD MMM YYYY)
 
Note: Documented cases of invasive aspergillosis or mucormycosis will be included (providing the patient meets all other study inclusion criteria), regardless of whether the diagnosis is classified as being “suspected” or confirmed via mycological or radiological assessments (this includes EORTC/MSG classification of “proven,” “probable,” and “possible” invasive fungal disease). All available sources will be used to confirm diagnosis (including any text in the medical records [eg, discharge diagnosis] and ICD-10 codes, if available). The level of documentation in the medical records is expected to vary by HCP and by site/country.
	At index date or closest assessment to index during the pre-index period. If no assessments are available in the pre-index period, then assessments closest to index in the post-index period will be used.
	
Mycological confirmation:
 
 • Yes; • No; • Unknown. 	
	Date of mycological confirmation (DD/MMM/YYYY) (if applicable)	
	Mycological examination type (if applicable):	

Category	Variable	Timepoint
	
 • Blood or tissue culture; • Bronchoalveolar lavage; • Urine sample; • Biopsy specimen; • Other (specify); • Unknown. 	
	
Radiological confirmation:
 
 • Yes; • No; • Unknown. 	
	
Date of radiological confirmation (DD/MMM/YYYY) (if applicable)
	
	
Radiological assessment type (if applicable):
 
 • Chest X-ray; • CT scan; • Ultrasound; • MRI; • Other (specify); • Unknown. 	
	
Radiographic assessment location:
 
 • Brain; • Lungs; • Liver; • Kidney; • Stomach; • Intestines; • Other (specify); • Unknown. 	
	
Other confirmation type:
 
 • Yes (specify); • No; • Unknown. 	
	
EORTC/MSG disease classification (if available):
 
 • Proven; • Probable; • Possible; • Unknown. 	
	
Localization (all that apply):
 
 • Lungs; • Sinus; 	

Category	Variable	Timepoint
	
 • Skin; • Stomach; • Intestines; • Central nervous system; • Bones; • Liver; • Kidney; • Blood; • Other (specify); • Unknown. 	
Antifungal drug use prior to index treatment	
Antifungal type:
 
 • Liposomal amphotericin B; • Voriconazole; • Posaconazole; • Caspofungin; • Anidulafungin; • Micafungin; • Other (specify); • Unknown. 	1 year prior to index date
	
Reason for switch to index treatment (if applicable):
 
 • Lack of response to treatment; • AE; • Patient decision (unrelated to AEs); • Other (specify); • Unknown. 	
	Date of initiation (DD MMM YYYY)	
	Date of discontinuation (DD MMM YYYY)	
Other prior treatment history	
 • Antibiotic (specify); • Surgery (specify); • Corticosteroid (specify); • Immunosuppressant (specify); • Chemotherapy (specify); • Other (specify); • Unknown. 	30 days prior to index date

AE = adverse event; COPD = chronic obstructive pulmonary disease; CT = computed tomography; EORTC/MSG = European Organization for Research and Treatment of Cancer/Mycosis Study Group; HCP = healthcare provider; ICD-10 = *International Classification of Diseases, 10th Revision*; MRI = magnetic resonance imaging.

9.4.2. Isavuconazole Treatment Patterns

Category	Variable	Timepoint
Index treatment (isavuconazole) administration	
Setting of treatment administration:
 
 • Inpatient setting: 
 • Oncology ward; • Hematology ward; • Transplantation ward; • ICU; • General medicine ward; • Other ward (specify). • Outpatient setting; • Other (specify); • Unknown. 	Index date, post-index period
	
Loading-dose method of administration:
 
 • Infusion; • Oral; • Unknown; • Not applicable. 	
	
Date of first loading-dose administration (DD MMM YYYY)
	
	
Date of last loading-dose administration (DD MMM YYYY)
	
	
Loading dose:
 
 • 372 mg of isavuconazonium sulfate; • Other (specify). 	
	
Loading-dose frequency:
 
 • Every 8 hours for 48 hours (ie, 6 doses); • Other (specify). 	
	
Maintenance therapy method of administration:
 
 • Infusion; • Oral; • Maintenance therapy not administered; • Unknown; • Not applicable. 	
	
Date of first dose of maintenance therapy (DD MMM YYYY)
	
	
Date of last dose of maintenance therapy (DD MMM YYYY)
	
	
Maintenance dose (mg):
 
 • 372 mg of isavuconazonium sulfate; 	

Category	Variable	Timepoint
	
 • Other (specify). 
Maintenance dose frequency:
 
 • Every 24 hours (ie, once daily); • Other (specify). 	
Modification of index treatment	
Treatment modification (eg, dose adjustment, mode of administration change):
 
 • Yes; • No; • Unknown. 	Post-index period
	
Date of index therapy modification (DD MMM YYYY)
 
Type of therapy modification (all that apply):
 
 • Change from infusion to oral capsule; • Change from oral capsule to infusion; • Dose increase; • Dose decrease; • Frequency increase; • Frequency decrease; • Other (specify); • Unknown. 	
	
Reason for index therapy modification:
 
 • Lack of response to treatment; • AE; • Patient decision (unrelated to AEs); • TDM; • Drug-drug interaction; • Other (specify); • Unknown. 	
TDM	
Was TDM conducted?
 
 • Yes; • No; • Unknown. 
Date of TDM (DD MMM YYYY)
 
Outcome of TDM:
 
 • Treatment modification; • Treatment discontinuation; • None; • Other (specify); 	Post-index period

Category	Variable	Timepoint
Discontinuation of index treatment	
 Unknown. 
Discontinuation of index treatment:
 
 Yes; No; Unknown. 	Post-index period
	Date of discontinuation (DD MMM YYYY)	
	Reason for discontinuation:	
	
 Patient completed planned course of treatment; Lack of response to treatment; AE; Patient decision (unrelated to AEs); Treatment success (resolution of invasive fungal infection); Death (unrelated to therapy); TDM; Drug-drug interaction; Other (specify); Unknown. 	
Switch to a new antifungal drug after discontinuation of index treatment	
Switch to a new antifungal agent after discontinuation:
 
 Yes; No; Unknown. 	Post-index period
	Start date of subsequent antifungal agent (DD MMM YYYY)	
	End date of subsequent antifungal agent (DD MMM YYYY)	
	Type of new antifungal agent:	
	
 Liposomal amphotericin B; Voriconazole; Posaconazole; Caspofungin; Anidulafungin; Micafungin; Other (specify); Unknown. 	
Other subsequent antifungal use after end of index treatment	Type of new antifungal drug:	Post-index period
	
 Liposomal amphotericin B; Voriconazole; Posaconazole; 	

Category	Variable	Timepoint
	
 • Caspofungin; • Anidulafungin; • Other (specify); • Unknown. 	
	Start date of subsequent antifungal agent (DD MMM YYYY)	
	End date of subsequent antifungal agent (DD MMM YYYY)	
Index treatment administered as part of antifungal combination therapy	
Index treatment administered as part of antifungal combination therapy:
 
 • Yes; • No; • Unknown. 
Type of therapy administered in combination with isavuconazole:
 
 • Liposomal amphotericin B; • Voriconazole; • Posaconazole; • Caspofungin; • Anidulafungin; • Micafungin; • Other (specify); • Unknown. 	Index date, post-index period
	Start date of therapy administered in combination with isavuconazole (DD MMM YYYY)	
	End date of therapy administered in combination with isavuconazole (DD MMM YYYY)	
Other concomitant treatments (not including combination therapy)	
 • Antibiotic agent (specify); • Corticosteroid agent (specify); • Immunosuppressant agent (specify); • Chemotherapy (specify); • Other (specify); • Unknown. 	Index date, post-index period
	Start date of concomitant treatment (DD MMM YYYY)	
	End date of concomitant treatment (DD MMM YYYY)	

AE = adverse event; ICU = intensive care unit; TDM = therapeutic drug monitoring.

9.4.3. Clinical Effectiveness

Category	Variable	Timepoint
Clinical response ⁿ	Date of assessment (DD MMM YYYY) Clinical response status documented in the medical chart: 
• Clinical response;• Clinical failure;• Unknown.	Post-index period
Re-activation of same or new infection	Re-activation documented in the medical chart: 
• Yes;• No. Assessment date (DD MMM YYYY)	Post-index period
Radiological assessments	Radiographic assessment date (DD MMM YYYY) Radiographic examination type: 
• Chest X-ray;• CT scan;• Ultrasound;• MRI;• Other (specify);• Unknown. Radiographic examination location 
• Brain;• Lungs;• Liver;• Kidney;• Stomach;• Intestines;• Other (specify);• Unknown.	Post-index period
Radiological response ^o	Radiological examination date (DD MMM YYYY)	Post-index period

ⁿ Clinical response will be evaluated according to the following mutually exclusive modalities: Clinical response: resolution or partial resolution of all attributable clinical symptoms and physical findings. Clinical failure: no resolution of any attributable clinical symptoms and physical findings and/or worsening. When medical record documentation is not clear for the abstractor on which categories to specify, the investigator should review all available medical record documentation to determine classifications. If the investigator determines there is not enough medical record documentation to make the classification, they will indicate unknown. Since clinical response classification is important to the study, participating sites will be selected for participation in the study based on reporting to have diligent medical record documentation for response.

^o Radiological response will be evaluated according to the following criteria: Radiological response: ≥ 50% improvement from initial assessment, or improvement of at least 25% from the initial assessment for the follow-up at 6 weeks (ie, Day 42 [\pm 14 days]) or if end of treatment occurred before this time. When medical record documentation is not clear for the abstractor on which categories to

Category	Variable	Timepoint
	Radiological examination type 
 • Chest X-ray; • CT scan; • Ultrasound; • MRI; • Other (specify); • Unknown. 	
	Radiological response documented in the medical chart: 
 • Yes; • No; • Not applicable (initial assessment); • Unknown. 	
Mycological assessments	Mycological examination date (DD MMM YYYY)	Post-index period
	Mycological examination type: 
 • Blood or tissue culture; • Bronchoalveolar lavage; • Urine sample; • Biopsy specimen; • Other (specify); • Unknown. 	
Mycological response ^p	Mycological examination date (DD MMM YYYY)	Post-index period
	Mycological examination type: 
 • Blood or tissue culture; • Bronchoalveolar lavage; • Urine sample; • Biopsy specimen; • Other (specify); • Unknown. 	
	
 • Eradication; • Presumed eradication; 	

specify, the investigator should review all available medical record documentation to determine classifications. If the investigator determines there is not enough medical record documentation to make the classification, they will indicate unknown. Since radiological response classification is important to the study, participating sites will be selected for participation in the study based on reporting to have diligent medical record documentation for response.

^p Mycological response will be evaluated according to the following criteria: **eradication** or **presumed eradication** of the original causative organism cultured. **Failure** will be defined as persistence or presumed persistence. When medical record documentation is not clear for the abstractor on which categories to specify, the investigator should review all available medical record documentation to determine classifications. If the investigator determines there is not enough medical record documentation to make the classification, they will indicate unknown. Since mycological response classification is important to the study, participating sites will be selected for participation in the study based on reporting to have diligent medical record documentation for response.

Category	Variable	Timepoint
	
 • Failure; • Not applicable (initial assessment); • Unknown. 	
Biomarkers	
 • Galactomannan (GM), Serum; • Galactomannan (GM), Bronchoalveolar lavage (BAL); • (1→3)-β-D-Glucan (BDG), serum. • Test date (DD MMM YYYY). 	Index date, post-index period

CT = computed tomography; MRI = magnetic resonance imaging.

9.4.4. Safety

Category	Variable	Timepoint
AEs	
Type of event (documented by ICD-9 code, ICD-10 code or record in the medical chart):
 
 • Blood and lymphatic AE: 
 • Neutropenia; • Thrombocytopenia; • Pancytopenia; • Leukopenia; • Anemia; • Other (specify). • Immune system AE: 
 • Hypersensitivity; • Other (specify). • Metabolism and nutrition AE: 
 • Hypokalemia; • Decreased appetite; • Hypomagnesemia; • Hypoglycemia; • Hypoalbuminemia; • Malnutrition; • Other (specify). • Psychiatric AE: 
 • Delirium; • Depression; • Insomnia; • Other (specify); • Nervous system AE: 
 • Headache; • Somnolence; • Convulsion; 	Index date, post-index period

Category	Variable	Timepoint
	
 • Syncope; • Dizziness; • Paresthesia; • Encephalopathy; • Presyncope; • Peripheral neuropathy; • Dysgeusia; • Other (specify). • Ear and labyrinth AE: 
 • Vertigo; • Other (specify). • Cardiac AE: 
 • Atrial fibrillation; • Tachycardia; • Bradycardia; • Palpitations; • Atrial flutter; • Electrocardiogram QT shortened; • Supraventricular tachycardia; • Ventricular extrasystoles; • Supraventricular extrasystoles; • Other (specify). • Vascular AE: 
 • Thrombophlebitis; • Circulatory collapse; • Hypotension; • Other (specify). • Respiratory, thoracic and mediastinal AE: 
 • Dyspnea; • Acute respiratory failure; • Bronchospasm; • Tachypnoea; • Hemoptysis; • Epistaxis; • Other (specify). • Gastrointestinal AE: 
 • Vomiting; • Diarrhea; • Nausea; • Abdominal pain; 	

Category	Variable	Timepoint
	
 • Dyspepsia; • Constipation; • Abdominal distension; • Other (specify). • Hepatobiliary AE: 
 • Elevated liver chemistry tests (alanine aminotransferase [ALT], aspartate aminotransferase [AST], alkaline phosphatase, bilirubin); • Hepatomegaly; • Hepatitis; • Other (specify). • Skin and subcutaneous tissue AE: 
 • Rash; • Pruritus; • Petechiae; • Alopecia; • Drug eruption; • Dermatitis; • Other (specify). • Musculoskeletal and connective tissue AE: 
 • Back pain; • Other (specify). • Renal and urinary AE: 
 • Renal failure; • Other (specify). • General disorders and administration site condition AE: 
 • Chest pain; • Fatigue; • Injection site reaction; • Edema peripheral; • Malaise; • Asthenia; • Other (specify). • Other AE (specify). 	
AE onset date (DD MMM YYYY)		
AE resolution:		

 • Yes; • No; 		

Category	Variable	Timepoint
	
 • Unknown. 
AE resolution date (DD MMM YYYY)
	
	
AE seriousness:
 
 • Was life-threatening; • Required inpatient hospitalization or prolongation of existing hospitalization; • Resulted in persistent or significant incapacity or disability; • Was a congenital anomaly/birth defect; • Was a medically important event; • Resulted in death; • None of the above; • Unknown. 	
	
AE severity:
 
 • Mild; • Moderate; • Severe; • Unknown. 	
	
Documented relationship to isavuconazole:
 
 • Yes; • No; • Unknown. 
Action taken with isavuconazole:
 
 • Treatment discontinuation; • Dose reduced; • Dose increased; • Dose delayed; • Dose not changed; • Not applicable; • Unknown. 	
	
Outcome of event:
 
 • Resolved; • Resolving; • Resolved with sequelae; • Not resolved; • Fatal; • Unknown. 	

AE = adverse event; ICD-9 = International Classification of Diseases, 9th Revision; ICD-10 = International Classification of Diseases, 10th Revision.

9.4.5. Survival Status

Category	Variable	Timepoint
Survival status	
Date of death (DD MMM YYYY)
 
Primary cause of death:
 
 • Complications related to invasive aspergillosis or mucormycosis; • Other disease complications; • SAE related to isavuconazole treatment; • SAE unrelated to isavuconazole treatment; • Other (specify); • Unknown. 	Post-index period

SAE = serious adverse event.

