9.9.2. Planned Analysis

9.9.2.1. Analysis Plan for Primary Objectives

Mortality/survival rates will be summarized and reported. Clinical, radiological, and mycological response documented in the medical record will be summarized using proportions and counts for each category. Details of radiological and mycological assessments will be reported in a descriptive manner, including the type of assessment and the assessment findings. Definitions of response will be provided in the SAP. Time to response and all-cause mortality will be analyzed using the KM method and quartiles and 95% CIs will be reported.

Descriptive statistics will be used to describe all AEs and SAEs reported during the medical record review. The safety data described will include event type, relationship to isavuconazole treatment (where known), event severity, event seriousness, action taken with isavuconazole treatment and outcome of the event. Definitions of AEs and SAEs will be described in the SAP. Time from index treatment to first AE onset will be summarized.

Key timepoints of interest for assessment of treatment effectiveness, safety and survival outcomes will be at 6 weeks, 12 weeks, and 24 weeks after initiation of index treatment. In the cases that usual care visits do not directly coincide with these timepoints, the time windows for assessment of outcomes will be defined in the SAP.

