### 6.3 ANALYSIS OF CLINICAL OUTCOMES

Each clinical outcome will be analyzed using counts and frequencies at weeks 6, 12, and 24, along with other descriptive information about the clinical outcome itself.

Additionally, time-to-event analyses anchored on the index date of isavuconazole initiation will be performed using the KM method. For each clinical outcome, the time-to-event analyses will result in a KM plot with summary statistics, including survival-time quartiles and KM estimates at weeks 6, 12, and 24 with accompanying 95% CIs. All analyses will be performed for invasive aspergillosis patients, mucormycosis patients, and for the total study population. If subgroup analyses are pursued, Cox regression will be employed to derive HRs and accompanying 95% CIs.

For the death outcome, patients will be categorized as dead, alive, or unknown at each timepoint of interest, and primary cause of death will be tabulated (Appendix 1, Analysis Table 5.1). For KM analyses, a documented death will comprise the event, and patients will be censored at the date when they are last known to be alive (Appendix 1, Analysis Figure 1; Appendix 1, Analysis Table 5.2).

For the clinical response outcome, patients will be categorized as having clinical success, having clinical failure, or unknown response at each timepoint of interest will be tabulated (Appendix 1, Analysis Table 6.1). In addition, rates of reactivation of the same infection and rates of new infection will be documented overall and specific to whether these events occurred during isavuconazole treatment. For KM analyses, clinical response will comprise the event, and patients will be censored at the earliest timepoint of any of the following: loss to follow-up, end of study, or death (Appendix 1, Analysis Figure 2; Appendix 1, Analysis Table 6.2).

For radiological response, patients will be categorized as having a success, not having a response, unknown response, or not applicable (for the first assessment) at the relevant timepoints of interest (Appendix 1, Analysis Table 7.1). Additionally, radiological examination type and bodily location of the examination will be tabulated. For KM analyses, radiological response will comprise the event, and patients will be censored at the earliest timepoint of any of the following: loss to follow-up, end of study, or death (Appendix 1, Analysis Figure 3; Appendix 1, Analysis Table 7.2).

PFIZER CONFIDENTIAL

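### The cause-of-death codes are not mutually exclusive, so the planned descriptive table cannot give a unique count of deaths from the treated infection; all-cause mortality is unaffected

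*Protocol*

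**What the plan says.** Protocol 9.4.5 has a single field, "Primary cause of death", with six options: "Complications related to invasive aspergillosis or mucormycosis", "Other disease complications", "SAE related to isavuconazole treatment", "SAE unrelated to isavuconazole treatment", other (to be specified) and unknown. It gives no order of precedence and no rule separating the disease codes from the SAE codes.

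Three other places bear on what counts as an SAE:

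- Protocol 9.4.4 lists "Resulted in death" among the criteria that make an adverse event serious.
- Protocol 9.9.2.1 states: "Definitions of AEs and SAEs will be described in the SAP". SAP Table 1 then defines an SAE as any SAE found in the record or described by ICD codes. This is circular and excludes nothing due to the infection or the underlying illness.
- Protocol 9.4.6 accepts an adverse event arising from the fungal disease as a reason for hospitalization.

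SAP 6.3 says that "primary cause of death will be tabulated", in Analysis Table 5.1. The same section takes any documented death as the event in the Kaplan-Meier analysis of mortality.

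**The concern.** The list combines two separate questions: which disease killed the patient, and whether the drug was responsible. A fatal complication of aspergillosis that the drug did not cause can be read as belonging to the fungal code and also to the unrelated-SAE code. A fatal complication of leukaemia can likewise be read as other disease or as an unrelated SAE.

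The study has no comparator, and its patients are expected to have severe underlying disease (protocol 9.11). A reader of the mortality result will want to know how many deaths came from the treated infection, and the cause-of-death table is the planned display that addresses this directly. If staff at some 22 sites in five countries resolve the overlap differently, differences in coding could look like differences in cause of death.

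**Working it through.** The plan states no cause-specific figure, so there is none to reproduce. The check is mainly a comparison of texts.

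**1. Can one death carry two valid codes?**

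- A death from a disease complication, not caused by the drug, fits one of the two disease codes by their plain wording.
- If that complication is recorded as an adverse event, protocol 9.4.4 makes it serious because it was fatal. As it is not drug-related, it also fits the unrelated-SAE code.
- The condition that the complication is recorded as an adverse event is not ruled out. SAP Table 1 has no exclusion, protocol 9.4.6 recognises adverse events arising from the fungal disease, and the checklist in 9.4.4 includes acute respiratory failure and hemoptysis without excluding cases due to infection.

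Double eligibility is therefore possible, though not stated to be general.

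**2. Does any visible rule resolve it?** Clinical, radiological and mycological response each have criteria and an investigator-review step for unclear records (protocol 9.4.3, SAP Table 1). Cause of death has neither. SAP Table 1 takes death as the abstraction form gives it.

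There is also a smaller mismatch. In 9.4.4 the relation of an adverse event to the drug may be unknown, but 9.4.5 offers an SAE death only as related or unrelated.

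**3. What is affected?** All-cause mortality counts every death, so moving a death between codes changes no primary count, Kaplan-Meier estimate or confidence interval. Only the cause distribution moves.

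**4. Illustration of sensitivity.** Inputs from protocol 9.5 and 9.1: 19% day-42 mortality (the aspergillosis rate from the SECURE trial, applied here by assumption to the mixed cohort), a target of 600 patients and a minimum of 200. Deaths: D = 0.19 × 600 = 114, or 0.19 × 200 = 38.

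Let f be the true fungal share of deaths and s the share of fungal deaths coded as unrelated SAE. Both are assumptions; the documents give neither. Deaths coded fungal = D × f × (1 − s). For D = 114 and f = 0.5:

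| s | Coded fungal deaths | Share of deaths | All-cause mortality |
|---|---|---|---|
| 0 | 57 | 50% | 19% |
| 0.25 | 42.75 | 37.5% | 19% |
| 0.50 | 28.5 | 25% | 19% |
| 1 | 0 | 0% | 19% |

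With s = 0.5 and f from 0.3 to 0.7, the coded share runs from 0.3 × 0.5 = 15% to 0.7 × 0.5 = 35%.

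**5. Bounds.** Suppose the fungal code is used only for true fungal deaths and no fungal death is coded as other disease or as a drug-related SAE. The fungal count is then a lower bound. Adding the unrelated-SAE, other and unknown codes gives an upper bound. For example, let a share u of the non-fungal deaths also go to unrelated SAE, with none coded other or unknown:

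- lower share = f(1 − s) = 0.5 × 0.75 = 37.5% (42.75 of 114)
- upper share = f + (1 − f)u = 0.5 + 0.5 × 0.25 = 62.5% (71.25 of 114)

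The table still carries information, but it does not fix a single value.

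**6. Mucormycosis.** If the cohort resembled the 37 patients in the VITAL trial at 33% mortality (protocol 9.5), there would be 0.33 × 37 ≈ 12 deaths. Recoding one would move the distribution by 1/12, or about 8 percentage points.

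**The case against.** The strongest reply is that the field asks for one primary cause. An abstractor would naturally use a specific disease code first and keep unrelated SAE for events that are neither disease complications nor drug effects. SAP Table 1 also requires the chart to document an SAE, and a death from progressive infection may never be written up as one. This reading is reasonable, but it is not written down, and the rest of the text does not compel it.

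A reader might infer that every fatal fungal or underlying-disease complication is also an unrelated SAE. The documents do not support that. The seriousness criterion applies to events already classed as adverse events and does not turn a disease complication into one.

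A reader might also infer that the table says nothing about infection deaths, or that the primary mortality result is compromised. Neither follows. Bounds remain available under the assumptions above, and all-cause mortality ignores the code. No objective or analysis targets deaths attributable to the infection. Other collected data (adverse-event type, relation and outcome, and the response assessments) also bear on the cause.

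Three further points stand. The illustration moves deaths only out of the fungal code; abstractors could equally assign ambiguous deaths to it, so the net direction is unknown. The abstraction-form instructions and the Appendix 1 table shells are not in the text, and the CRO trains the sites, so a coding rule may exist there. Uneven documentation across sites is already a declared limitation (protocol 9.11).

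**Conclusion.** The concern holds in a limited form. The code list in protocol 9.4.5 allows two valid codes for the same non-drug disease death, and no rule in the protocol or SAP text chooses between them. This is a flaw in the list itself, since the SAP tabulates the codes as entered. The consequence is confined to one descriptive table, which loses a unique count of infection deaths and may vary with site habit. The size and net direction of that variation cannot be estimated from the documents; the percentages above rest on assumed fungal shares and coding rates and show sensitivity only. The conclusion also assumes that no precedence rule exists in material outside the text. The change is worth making because it is cheap, but the primary analysis does not depend on it.

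**What to change.** Preferred: split the item into two.

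1. Underlying cause of death: invasive aspergillosis or mucormycosis; underlying or other disease; other (specify); unknown.
2. Death due to an isavuconazole-related SAE: yes; no; unknown.

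This also gives a place to a fatal SAE of unknown relation.

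Alternative: keep the single item, restrict the unrelated-SAE code to events due neither to the fungal infection nor to other disease, and state that the disease codes take precedence.

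If the form is already fixed, add to SAP 6.3 that deaths with the unrelated-SAE code are queried to the site investigator for reclassification. Leave those that cannot be resolved unclassified, and report the fungal-death count with lower and upper bounds. Protocol 9.9 allows for this through a revised SAP before data collection is complete.

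Do not reassign deaths centrally from the adverse-event term: a term such as acute respiratory failure does not show whether the infection or the underlying disease was the cause, so this could add misclassification. No new fungal-mortality outcome at weeks 6, 12 and 24 is needed, because no objective asks for one.

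The cost is one form edit or one SAP rule, with slightly more abstraction or query effort for patients who died.
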